- To evaluate the proposed symptom-based clinical response definition that uses the MACrO₂ PRO, to understand patient perspectives on meaningful change more generally, through qualitative embedded interviews

Phase 3 Part of the Study:

Primary Objective in Phase 3

- *[In the US:]* To determine if eptraborole + OBR is superior to placebo + OBR in symptom-based clinical response as measured by the MACrO₂ PRO (the use of this PRO instrument in Phase 3 will be confirmed after Phase 2 analysis)
- *[Outside the US:]* To determine if eptraborole + OBR is superior to placebo + OBR in microbiological response

Secondary Objectives in Phase 3

- *[In the US:]* To determine if eptraborole + OBR is superior to placebo + OBR in microbiological response (key secondary objective)
- *[Outside the US:]* To determine if eptraborole + OBR is superior to placebo + OBR in symptom-based clinical response as measured by the MACrO₂ PRO (the use of this PRO instrument in Phase 3 will be confirmed after Phase 2 analysis) (key secondary objective)
- To assess concordance between PRO symptom/function-based clinical response and microbiological response
- To assess microbiological reinfection and relapse
- To assess the safety of oral eptraborole compared to placebo
- To assess the plasma PK of oral eptraborole

Exploratory Objectives in Phase 3

- To assess clinical and microbiological responses in subgroups (eg, age, ALIS use at baseline, presence/absence of any fibrocavitary disease, MAC resistance phenotype)
- To assess pulmonary radiological response
- To assess microbiological response by eptraborole MIC
- To evaluate postbaseline MAC isolates for decreased susceptibility to eptraborole compared to baseline
- To assess time to MACrO₂ PRO symptom-based clinical response
- To assess time to microbiological response

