2.2.6 Analysis Timing

In the Phase 2 part of the study, prespecified members of the Sponsor and [REDACTED] biostatistics analysis teams will be unblinded to treatment assignment for data analyses after the last patient in Phase 2 completes all assessments for the Month 6 visit (including the Month 6+1 week PRO assessment); however, study staff conducting psychometric validation analyses will remain blinded. Patients, Investigators, and other study staff not directly associated with the statistical analysis will also remain blinded to treatment assignment through the last study visit (LFU) (see Study Blinding Plan).

Initial Phase 2 data analyses will include review of patient-reported outcome responses (including clinical symptom responses and functional assessments), microbiological, safety, and PK data collected at multiple time points through Month 6. All efficacy and psychometric endpoints conducted as part of the Phase 2 Month 6 analysis will be considered final at this time. Any efficacy endpoint data collected at any visits beyond Month 6 (e.g. EOT, LFU) will not be summarized at the time of this analysis.

The Phase 2 part of the study includes a blinded analyses to assess the psychometric properties (ie, reliability, validity, ability to detect change, and clinically meaningful within-patient changes in scores) of the “MACrO2 PRO” instrument. A Psychometric Analysis Plan (PAP) is included as a separate document. The Phase 2 psychometric data analyses will support selection and positioning of PRO measures as endpoints for Phase 3. Decisions will be based on the magnitude of item-level or domain-level (when appropriate) change, ability to detect change (responsiveness), and concordance with microbiological response data. The definition of clinical response to be used in the Phase 3 part of the study will be informed through the psychometric analyses conducted with the pooled blinded data from the Phase 2 part of the study. In addition, the Sponsor will review the unblinded clinical and microbiological outcomes from Phase 2 data through Month 6 to determine if the sample size for Phase 3 should be adjusted.

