- *[Outside the US:]* Key secondary endpoint: Pending verification from the Phase 2 part of the study: MACrO₂ PRO symptom-based clinical response, defined as improvement of ≥ 1 grade in the key symptom with no worsening of other symptoms between baseline and Month 6 in the Micro-ITT Population
- By-subject microbiological improvement at Month 3 and Month 6 using decrease in MAC colony counts of ≥ 1 category in the Micro-ITT Populations
- PRO symptom/function-based clinical response using mean changes in PRO domain scores (eg, QOL-B, NTM Symptoms Module, SGRQ-C), or improvement of ≥ 1 grade in the key symptom with no worsening of other symptoms in the MACrO₂ PRO, monthly through Month 6, in the Micro-ITT and Per-Protocol populations
- Concordance analysis of PRO symptom/function-based clinical response and microbiological response (by-subject sputum culture conversion and by-subject microbiological improvement) in the Micro-ITT Population
- Rates of reinfection (new pulmonary MAC infection caused by strain[s] different from the baseline MAC isolate) and relapse (pulmonary MAC infection caused by the same baseline MAC isolate) at Month 6, EOT, and LFU in the Micro-ITT Population
- Assessment of TEAEs and changes from baseline in clinical laboratory values, ECGs, and vital sign changes in the Safety Population
- Characterization of epetaborole plasma PK in the PK Population

Exploratory Endpoints for Phase 3:

- Clinical response and microbiological response (by-subject sputum culture conversion and by-subject microbiological improvement) at Month 3 and Month 6 presented by age category, presence/absence of any fibrocavitary disease, ALIS use at baseline, and MAC resistance phenotype (macrolide-resistant and amikacin-resistant) in the Micro-ITT Population
- Radiographic response at Month 6 and EOT, defined as overall change from baseline based on blinded central reading of chest CT in the Micro-ITT Population
- By-subject microbiological response (by-subject sputum culture conversion and by-subject microbiological improvement) by epetaborole MIC at Month 6 in the Micro-ITT Population
- Rate of decreased susceptibility among postbaseline MAC isolates, defined as a ≥ 4 -fold increase in epetaborole MIC relative to the baseline isolate MIC, among patients remaining MAC culture-positive at Month 4 or later in the Micro-ITT Population
- Time (in days) to improvement in PRO-based clinical response in the Micro-ITT Population

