 - For analyses of domain scores or total scores, a longitudinal analysis will be performed which will include data recorded at all time points up to Month 6 and will provide estimates of treatment effect at the relevant time points (Months 3 and 6). Missing data is not expected, but if there is a larger than expected amount of missing data, further analyses to assess the impact of missing data may be undertaken using missing data imputation methods.

- For analyses of QOL-B response, NTM Symptoms Module response, and SGRQ-C response, a patient will be considered to have missing data if the relevant score is not completed at the protocol-defined time points of Month 3 and Month 6. Patients with missing Month 3 or Month 6 data will be defined as an indeterminate response at the corresponding time point (Month 3 or Month 6), and will be considered clinical non-responders. For model-based analyses of PRO measures over time, patients with one or more missing visits will be retained in the model, with no imputation methods applied to those missing results.
- Missing microbiological culture data:
 - For patients with no available sputum for culture despite attempted sputum collection — and if the patient was previously sputum culture negative for MAC at their last post-baseline available monthly assessment — the microbiological outcome will be assessed as culture negative for that visit and the MAC colony count category will be assessed as “No growth on agar or broth” at that visit. All other patients with missing sputum culture results that impacted the ability to assess sputum culture conversion (i.e., 3 consecutive months of negative sputum cultures) or categorical decreases in MAC colony counts will be considered microbiological non-responders.
- Missing colony count data:

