in QOL-B respiratory domain score of ≥ 8 based on a minimally clinically important difference (MCID) established for bronchiectasis patients ([Quittner 2015b](#)), as well as by a threshold (11.1 points) determined as part of a blinded anchor-based psychometric analysis of the observed QOL-B respiratory domain scores from Phase 2 patients across pooled treatment arms and visits as a potentially more specific indicator of meaningful improvement in treatment-refractory MAC patients. Similarly, response in MACrO₂ total scaled score is defined as an improvement (decrease in total score) by a threshold (11.3 points) determined as part of a blinded anchor-based psychometric analysis of the observed total scaled scores from Phase 2 patients across pooled treatment arms and visits as an indicator of holistic symptom-based improvement in treatment-refractory MAC patients. Response in SGRQ-C total score is defined as an improvement in SGRQ-C total score of ≥ 4 based on a MCID established for COPD patients ([Jones 2023](#)). A corresponding threshold for a response endpoint in the NTM Symptoms domain of the NTM Module has not been defined, as an MCID has yet to be clearly established for this endpoint, but this study will investigate distribution-based minimal important differences (MIDs) using $0.5 \times$ baseline SD and the standard error of the mean (SEM) of the baseline measurement, where in both cases baseline is pooled across both treatment groups in the Micro-ITT Population, as experimental response thresholds. Response in PGIS or CGIS at each post-baseline visit is defined as a reduction in severity of one or more grades relative to baseline. Response in PGIC or CGIC at each post-baseline visit is defined as a reported change of severity category of “Much Better” or “A Little Better.” For all of the above PRO response definitions, missing results at the given timepoint will be considered failures in the Micro-ITT analysis.

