Clinical response as defined above for each individual PRO endpoint point (QOL-B respiratory domain, MACrO₂ original responder definition and response in total scaled score by threshold, SGRQ-C, NTM Symptoms Module, PGIS, CGIS, PGIC, and CGIC) will be presented dichotomously (Yes/No) for each treatment arm and will be presented as the treatment difference and associated 95% confidence interval and p-value, calculated using the method of Miettinen and Nurminen stratified by baseline use of ALIS and the presence or absence of any fibrocavitary disease for both the Micro-ITT and PP populations. In addition, to examine the influence of baseline severity on the treatment effect, clinical response rate by month will also be analyzed using a logistic regression model, including treatment and baseline key symptom severity (for MACrO₂ original responder definition only), baseline score (for QOL-B respiratory domain, MACrO₂ total scaled score, SGRQ-C Total Score, NTM Symptoms Domain), baseline severity in CGIS (for CGIS and CGIC), or baseline severity in PGIS (for PGIS and PGIC) as covariates. Stratification factors of baseline ALIS use and the presence or absence of any fibrocavitary disease will also be included as covariates in each model. For each logistic regression model, the estimated odds ratio and 95% confidence interval and corresponding p-value for the treatment effect will be presented.

Line plots of mean score (\pm SD) as well as mean (\pm SD) change from baseline in score over time will be produced for continuous PROs (e.g., QOL-B domain scores, MACrO₂ total scaled score, NTM symptom module score and total SGRQ-C score), with the two treatment groups indicated with different colors on the plot. A bar plot of categorical PROs (e.g., proportion of MACrO₂ responders, PGIS, PGIC, CGIS, CGIC and Meaningful Change Question) by treatment group will also be produced by visit.

In order to assess the concordance of PRO changes with microbiological changes the following summaries will be produced for each PRO. These will be produced at Month 3 and 6, as specifically noted below:

- Summary of PRO response (Response/Failure) versus sputum culture conversion (Conversion/No Conversion) by Month 6
- Summary of PRO response (Response/Failure) at Month 3 versus sputum culture conversion (Conversion/No Conversion) by Month 6

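### Phase 3 concordance tables can count a patient lost before conversion as an agreeing pair, because a missing PRO and missing cultures are both scored as non-response

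*SAP*

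**What the plan says.** SAP 2.1 lists among the Phase 3 secondary objectives "To assess concordance between PRO symptom/function-based clinical response and microbiological response". SAP 2.3 places the matching endpoint, "Concordance analysis of PRO symptom/function-based clinical response and microbiological response", in the Micro-ITT Population.

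SAP 3.4.3.3 gives the displays:

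- "Summary of PRO response (Response/Failure) versus sputum culture conversion (Conversion/No Conversion) by Month 6", and a second table that sets Month 3 PRO response against conversion by Month 6. Both have two levels per axis.
- PRO response against microbiological improvement. The only extra level is for a missing baseline colony count.
- PRO response against colony-count category. This has a Missing level, but only on the culture axis.
- Scatterplots of colony-count category against change in continuous PRO score.

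Two missing-data rules feed these tables. For PRO response, SAP 3.4.3.3 states that "missing results at the given timepoint will be considered failures in the Micro-ITT analysis". For cultures, SAP 3.1.4 has an exception and a default. The exception covers attempted collection that yields no sputum when the last available post-baseline culture was negative: "the microbiological outcome will be assessed as culture negative for that visit". The default reads "All other patients with missing sputum culture results that impacted the ability to assess sputum culture conversion" and continues to "categorical decreases in MAC colony counts will be considered microbiological non-responders".

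The Phase 3 concordance text does not restate the population or the missing-data rule. It gives no observed-only version and no agreement statistic.

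**The concern.** Scoring missing as failure is a defensible, usually conservative choice when two arms are compared. A concordance table asks something else: whether two outcomes move together within the same patient. Loss to follow-up removes both outcomes at once. If both are then scored as non-response, that common cause of missingness becomes agreement.

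The SAP treats the same gap differently elsewhere. Under SAP 3.4.3.1 a patient without complete baseline and Month 6 QOL-B respiratory scores is left out of the primary analysis under missing at random, apart from intercurrent-event cases. In the concordance tables the same missing Month 6 score becomes a failure.

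At stake is the reading of a stated secondary objective. A report could describe symptom and culture response as more concordant than the observed data show.

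**Working it through.** **1. Do the efficacy rules reach these tables?** SAP 2.3 sets the endpoint in Micro-ITT, and SAP 5 lists no change to that. The PRO rule is written for the Micro-ITT analysis and the culture rule for conversion and colony-count decrease generally. The tables' own level names leave nowhere else for a missing value. Inheritance is therefore an inference, but a firm one.

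**2. Who is affected?** Conversion needs three consecutive monthly negatives by Month 6 (SAP 3.4.3.2), so Month 3 is the earliest visit that can complete it. Protocol 3.1.1 and 4.4 plan only EOT and LFU assessments after study drug is stopped early.

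| Patient | Cell in the conversion table | Effect |
|---|---|---|
| Leaves before Month 3 | Failure / No Conversion, both tables | Agrees, by imputation |
| Leaves later, not converted, conversion still possible | Failure / No Conversion at Month 6 | Agrees, by imputation |
| Not converted, observed positives already rule out conversion, then leaves | Failure / No Conversion at Month 6 | Conversion status is real; only the PRO is imputed |
| Converts, then leaves before Month 6 | Failure / Conversion at Month 6 | Disagrees |
| Month 3 PRO responder, leaves before converting | Response / No Conversion in the Month 3 table | Disagrees |

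The third row arises, for example, with positives at Months 3 and 4, since every run of three months within Months 1 to 6 contains one of them. In the improvement table, a patient with a baseline count but neither PRO nor culture at the visit is Failure / No Improvement, unless the attempted-collection exception applies. That exception does not describe a patient who has left.

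**3. Inputs for an illustration.** The documents state no concordance figure and no Phase 3 missingness, so I borrow the planning figures in SAP 2.2.7: 124 and 62 patients, response 30% and 10%, two-sided alpha 0.05, about 90% power. That figure reproduces: 89.7% by normal approximation and 90.7% by exact enumeration of the unstratified Miettinen-Nurminen test. The pooled rate is (124 × 0.30 + 62 × 0.10) / 186 = 43.4 / 186 = 23.3%, used for both PRO response (p) and conversion (q). The fraction lost before conversion (d) is assumed.

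**4. Formulas.** With no association, agreement among observed patients is pq + (1 − p)(1 − q) = 0.054 + 0.588 = 0.642. Adding d to Failure / No Conversion gives apparent agreement A = (1 − d) × 0.642 + d. Both response margins become m = (1 − d) × 0.233. Chance agreement is E = m² + (1 − m)², and kappa = (A − E) / (1 − E).

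| d (assumed) | A | E | kappa |
|---|---|---|---|
| 0% | 64.2% | 64.2% | 0 |
| 10% | 67.8% | 66.8% | 0.03 |
| 20% | 71.4% | 69.6% | 0.06 |
| 30% | 75.0% | 72.7% | 0.08 |

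At d = 20% and N = 186, 37 of about 125 patients in Failure / No Conversion (30%) were never observed on both outcomes, and they make up 28% of all agreeing pairs.

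**5. Variations at d = 20%.**

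- True kappa 0.30: agreement moves from 75.0% to 80.0%, kappa from 0.30 to 0.34.
- No association, but 10% or 20% of those lost had already converted: agreement is 69.4% or 67.4%, and kappa 0.03 or 0.01.

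**The case against.** The strongest reply is that this is small and partly handled. The tables are descriptive, with no odds ratio, kappa or p-value planned. SAP 3.4 puts the endpoint outside the testing hierarchy and intends no claim from it. The colony-count table shows missing cultures, and the scatterplots do not turn a missing score into a failure. SAP 3.1.4 says missing data are not expected. All of this stands, and it limits the point to interpretation. It does not supply a missing level in the conversion and improvement tables.

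Three stronger readings are tempting.

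- A reader might infer that every dropout is an agreeing pair. The documents do not support that: the table in step 2 of the working shows two kinds of dropout that disagree and one whose non-conversion is genuinely observed.
- A reader might infer that the choice of Phase 3 PRO was distorted, because SAP 2.2.6 names among its criteria "ability to detect change (responsiveness), and concordance with microbiological response data". That criterion belongs to the Phase 2 psychometric work, which SAP 3.4 places in separate plans, and the choice has already been made. The Phase 3 tables cannot influence it.
- A reader might attach a larger effect using the pooled Phase 2 response of 25/78 (15/38 plus 10/40, SAP 1), or by taking a high missing fraction as known. SAP 3.4.1.1 already counts incomplete MACrO₂ assessments as failures, so 25/78 is not a rate among observed patients. As for missingness, Phase 3 enrollment began in September 2023 and the trial was terminated on 08 August 2024 (SAP 1). Low missingness cannot be presumed, but the documents do not say how many patients lacked Month 6 data.

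It is also fair that a both-observed table describes only retained patients, who may differ from those lost. That is a reason to show the missing counts beside it.

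**Conclusion.** The point holds in limited form. In the Phase 3 conversion and improvement tables, a patient lost before conversion with no PRO at the visit is scored as agreeing without both outcomes being observed, and apparent concordance is inflated.

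Under the stated assumptions (both rates 23.3%, no true association, 10% to 30% lost before conversion) raw agreement rises by about 4 to 11 percentage points and kappa by 0.03 to 0.08. The shift is clear in raw agreement and cell counts, modest in kappa, and smaller still if some of those lost had converted. The real size cannot be stated without the Phase 3 missing-data pattern. Type I error and the treatment comparisons are unaffected. It is a cheap improvement worth making before the Phase 3 tables are produced.

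**What to change.** Amend SAP 3.4.3.3 for Phase 3 only; SAP 1 limits changes after version 2.0 to Phase 3, and the Phase 2 Month 6 efficacy results are final. Either of these would do:

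- Add a Missing/Indeterminate level on both axes of the conversion and improvement tables, and on the PRO axis of the colony-count table.
- Add a version of each conversion and improvement table restricted to patients with an observed PRO at the visit and a culture status determined by observed cultures. For conversion, that means three consecutive observed negatives, or observed positives that rule them out by Month 6. For improvement, it means an observed result at baseline and at the visit.

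Keep the missing-as-failure versions for the treatment comparison. The cost is SAP wording and revised table shells, with no new data. The both-observed version has a smaller denominator and describes a retained subset, so the number excluded and the reason should be shown with it.

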- **EOT Visit:** The EOT Visit will be performed within 7 calendar days after the last dose of study drug. Patients requiring more than the maximum 16 months of MAC lung disease treatment for any reason will be discontinued from study drug and treated with an appropriate open-label antimycobacterial regimen at the discretion of the Investigator. EOT will occur up to 12 months after the first negative sputum culture for MAC (ie, the first month that defines sputum MAC culture conversion), or

at the time of premature discontinuation of study drug for any reason, including continued positive cultures despite 6 months of study drug therapy or any time after achievement of culture conversion. The EOT assessments may be performed during a regularly scheduled clinic visit if within the EOT window. For patients who are withdrawn from the study prior to completion, all the EOT Visit procedures will be performed at an Early Termination (ET) Visit.

- **LFU Visit:** The LFU Visit will be performed 3 months (84 days \pm 14 days) after the last dose of study drug.

Patients who are prematurely discontinued from study drug for any reason will remain in the study (ie, will not be withdrawn from the study) to undergo all scheduled EOT and LFU assessments, including safety assessments.

Microbiological methods are described in [Section 7.5.3](#) and additional details are presented in the Laboratory Manual.

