discontinued from study drug or withdrawn from the study prior to discussion with the Medical Monitor to determine if study drug should be continued beyond Month 6.

Patients who have microbiological recurrence, defined as positive sputum culture(s) any time after experiencing sputum conversion, should be continued on blinded study drug until additional data (eg, antibiotic susceptibility results and/or molecular typing) are available to determine whether the positive culture is due to relapse or reinfection (see [Section 7.5.3.4](#) for details regarding definitions and testing). Such cases should be discussed with the Medical Monitor *prior to* premature discontinuation of study drug ([Section 4.4](#)).

Unless the patient withdraws consent, patients who prematurely discontinue study drug will continue in the study for safety follow-up (ie, will not be withdrawn from the entire study) and will be assessed at the EOT and LFU visits.

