2.2 Study Design

2.2.1 Overview

Refer to Protocol Section 3.1 Summary of Study Design for full details of the study overview.

Briefly, this is a pivotal Phase 2/3, double-blind, placebo-controlled study of eptraborole + OBR versus placebo + OBR in patients with treatment-refractory MAC lung disease. This study will enroll adult patients with treatment-refractory MAC lung disease who meet all eligibility criteria.

This study features a sequential Phase 2/3 approach with an initial Phase 2 assessment of clinical responses (based on clinical symptoms and/or functional assessments), microbiological responses, safety, and PK associated with oral eptraborole, prior to the superiority analysis of oral eptraborole versus placebo in the Phase 3 part of the study.

In both the Phase 2 and Phase 3 parts of the study, each patient will complete multiple PRO measures including MACrO₂, QOL-B, NTM Symptoms Module, SGRQ-C, and global patient and clinician assessment scales (Patient Global Impression of Severity [PGIS], Patient Global Impression of Change [PGIC], Clinician Global Impression of Severity [CGIS], Clinician Global Impression of Change [CGIC]), and Meaningful Change Question (to be answered after each completion of the PGIC). An electronic PRO system will be used during the study to allow patients to complete the study questionnaires electronically.

The MACrO₂ PRO will be completed twice before the first dose of study drug to assess test-retest reliability (within 1 to 2 weeks prior to randomization, and on randomization day prior to study drug administration) and once weekly for the first 6 months of the study; other PROs and global assessment scales will be completed at baseline and once monthly for the first 6 months of the study. The QOL-B, NTM Symptoms Module, SGRQ-C, and PGIS will also be completed during Screening for test-retest reliability assessment. The PGIC, CGIC, and Meaningful Change Question will not be completed at baseline. After Month 6, all PROs will be completed every 3 months (84 days \pm 7 days), at End of Therapy (EOT), and at Late Follow Up (LFU). Sputum samples for microbiological assessments will be collected during the Screening period, once monthly for the first 6 months of the study, and then every 3 months (84 days \pm 7 days), at EOT, and at LFU.

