3.4.2 Phase 2 Efficacy Endpoints – End of Study Analysis

3.4.2.1 Phase 2 Secondary Efficacy Endpoints at End of Study Analysis

The secondary efficacy endpoints include rates of recurrence, reinfection, and relapse by End of Therapy and Late Follow-up. Rates of recurrence based on the definitions included in Section 3.4.1.3 will be presented by EOT and LFU in the Micro-ITT Population. Further subdivision into relapse versus reinfection within each definition of recurrence will be determined by whole genome sequencing prior to database lock.

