- Summary of PRO response (Response/Failure) versus microbiological improvement (Improvement/No Improvement/Non Applicable Due to Missing Baseline CFU Score)
- Summary of PRO response (Response/Failure) versus microbiological colony count culture categories (Missing, 0, 1, 2, 3, 4, 5, 6)
- Scatterplots of colony count category versus change from baseline in continuous PRO score, by treatment and by visit (Month 3 and Month 6)

Rates of microbiological recurrence, relapse, and reinfection following two different definitions will be presented by Month 6, by End of Therapy Visit, and by Late Follow-up Visit in the Micro-ITT Population. The primary analysis of recurrence, relapse, and reinfection will use the following definitions derived from the NTM-NET consensus statement ([van Ingen 2018](#)) regarding treatment outcome definitions in NTM pulmonary disease:

- Recurrence is defined as at least 1 MAC-positive culture on any media type (broth or agar) for 2 consecutive visits after culture conversion. Recurrence will be further categorized as either reinfection or relapse as follows:
 - Re-infection: at least 1 MAC-positive culture of a different species or the same species but a different strain of the causative species for 2 consecutive visits after culture conversion
 - Relapse: at least 1 MAC-positive culture of the same strain as the causative species for 2 consecutive visits after culture conversion

A sensitivity analysis will also be performed using the following definitions from the CONVERT trial ([Griffith 2021](#)):

- Recurrence is defined as having MAC-positive sputum cultures after culture conversion in liquid broth media (agar negative) for 3 or more consecutive visits, or having 1 MAC-positive sputum culture on solid media (LJ and/or 7H11 agar positive). Recurrence will be further categorized as either reinfection or relapse as follows:
 - Reinfection: new infection with a different MAC species or the same MAC species but a different strain from that isolated at baseline
 - Relapse: same MAC species and strain that was isolated at baseline

Subdivision into relapse versus reinfection within each definition of recurrence will be determined by whole genome sequencing when available. Identification of the overall recurrence, reinfection and relapse will be determined by a Sponsor Pathogen Review Committee in accordance with the Pathogen Review Plan.

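### The primary two-visit recurrence rule cannot count a first positive culture at late follow-up, so the by-LFU rate omits recurrence first detected there

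*SAP*

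**What the plan says.** SAP 3.4.3.3 sets the primary Phase 3 definition: "Recurrence is defined as at least 1 MAC-positive culture on any media type (broth or agar) for 2 consecutive visits after culture conversion". Its sub-categories repeat the condition, for example "Relapse: at least 1 MAC-positive culture of the same strain as the causative species for 2 consecutive visits after culture conversion". The rates are to be "presented by Month 6, by End of Therapy Visit, and by Late Follow-up Visit in the Micro-ITT Population".

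A sensitivity definition, taken from the CONVERT trial, asks for three or more consecutive visits when growth is in broth only, "or having 1 MAC-positive sputum culture on solid media (LJ and/or 7H11 agar positive").

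Phase 2 uses the same pair of definitions (SAP 3.4.1.3). Its later rates "will be presented by EOT and LFU in the Micro-ITT Population" (SAP 3.4.2.1).

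On the schedule, SAP 2.2.1 has sputum collected monthly to Month 6, then every 3 months, "at EOT, and at LFU". Protocol 3.1 says: "The EOT Visit will be performed within 7 calendar days after the last dose of study drug". It places LFU 84 days (±14) after the last dose, and Protocol 9.3 makes LFU the last protocol-specified visit. Patients who stop study drug early are seen only at EOT and LFU (Protocol 3.1.1 and 4.4). Neither document gives an exception for a single positive at the last visit or schedules a confirmatory sample after LFU.

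**The concern.** A rule that needs two consecutive positive visits works only where a further visit exists. At LFU there is none. The one visit well clear of study drug therefore adds no newly detected event to the primary rate.

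The stake is interpretation. A reader who sees the same primary rate by EOT and by LFU would naturally take it as evidence that conversion held after treatment stopped. For patients negative at EOT, the rule could not have shown anything else.

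**Working it through.** The plan states no recurrence rate, power or sample size for this endpoint, so there is no figure to reproduce. The check applies each rule to the planned visits.

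**Inputs.** Converters are treated for 12 months from the first negative month, up to 16 months (Protocol 3.1.1). Conversion needs three consecutive monthly negatives by Month 6, so the first negative falls at Month 1, 2, 3 or 4. If it falls at month k, the third negative is at k + 2, EOT is at k + 12 and LFU is at about k + 15.

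| First negative | Third negative | Sputum visits after conversion |
|---|---|---|
| Month 1 | Month 3 | Months 4, 5, 6, 9, 12; EOT (13); LFU (16) |
| Month 2 | Month 4 | Months 5, 6, 9, 12; EOT (14); LFU (17) |
| Month 3 | Month 5 | Months 6, 9, 12; EOT (15); LFU (18) |
| Month 4 | Month 6 | Months 9, 12, 15; EOT (16); LFU (19) |

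**Rules applied.** Every visit after the first positive is also taken as positive, which is the case most favourable to being counted. All four schedules give the same result:

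| First positive at | Primary, by EOT | Primary, by LFU | CONVERT by LFU, agar-positive | CONVERT by LFU, broth only |
|---|---|---|---|---|
| Last visit before EOT, or earlier | counted | counted | counted | counted |
| EOT | not counted | counted | counted | not counted |
| LFU | not counted (0 of 4) | not counted (0 of 4) | counted (4 of 4) | not counted (0 of 4) |

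**Why this is general.** The only consecutive pair that contains LFU is EOT with LFU. The step from the by-EOT to the by-LFU primary rate is therefore exactly the patients positive at both visits who had not already qualified. The argument does not use the number of earlier visits, so it also holds for converters who stop study drug early.

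**Length of the gap.** EOT falls 0 to 7 days after the last dose and LFU 70 to 98 days after it (84 ± 14). The interval between them is 63 days (70 − 7) to 98 days (98 − 0). A recurrence that first turns culture-positive in that window adds nothing to the primary rate.

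**Possible size, by assumption.** Let f be the share of converters first positive at LFU. The documents give no value. The share of the Micro-ITT Population left out is the conversion rate × f. The protocol's planning rates are 30% and 10% (Protocol 8.2.4). With f anywhere from 0 to an assumed 30%:

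- epetraborole: 0 to 0.30 × 0.30 = 9 percentage points;
- placebo: 0 to 0.10 × 0.30 = 3 percentage points.

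The primary rate picks up 0 points of this at every f. This is illustration only. SAP 1 reports that Phase 2 did not show superior conversion, so the planning rates may not apply.

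**The case against.** The two-visit rule is derived from a published consensus, and asking for confirmation is a sound guard against transient positives. That stands, and it is a reason to keep the rule.

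The SAP also reports every time point under two definitions, and the CONVERT one needs only a single agar-positive culture. That stands too. What is missed under both is a first positive at LFU in broth only. This is the lowest positive category in Protocol Table 1, but SAP 3.1.4 itself describes MAC growing in broth and not on agar as not uncommon.

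Determinations are made by a sponsor committee under a Pathogen Review Plan that is not among the documents. That plan might address last-visit positives, but it does not change the rule as written in the SAP.

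Four stronger readings are tempting but not supported:

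- *The primary analysis can show no post-treatment recurrence at all.* A patient first positive at EOT, which can be up to 7 days off drug, and again at LFU is newly counted by LFU.
- *The SAP contradicts the protocol's endpoint definition.* The wording "Patients who have microbiological recurrence, defined as positive sputum culture(s) any time after experiencing sputum conversion" belongs to an instruction on continuing study drug while typing is pending. The protocol's endpoint sections and 7.5.3.4 define relapse and reinfection by strain.
- *The by-Month-6 rate has the same flaw.* Patients whose third negative falls at Month 5 or 6 cannot qualify by Month 6, but their later confirmed recurrences enter the by-EOT or by-LFU rates.
- *Error control is affected.* The endpoint is outside the testing hierarchy, and SAP 3.4 intends no specific claim from it.

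**Conclusion.** The point holds for the rule as written. A first positive at LFU counts in 0 of 4 converter schedules under the primary definition, for recurrence, relapse and reinfection alike. Under the CONVERT definition it counts in 4 of 4 if agar-positive and 0 of 4 if broth-only. The primary by-LFU rate therefore cannot be read as off-drug durability for patients who were negative at EOT.

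How many patients this affects is unknown; the 30% upper value for f is an assumption. The conclusion itself rests only on LFU being the last visit and on there being no last-visit exception, in the SAP or in the unseen Pathogen Review Plan. It also assumes that unscheduled sputum after LFU does not count as a visit, on which the SAP is silent. The consequence is for interpretation of a secondary endpoint, so the change should be made but does not bear on the trial's formal tests.

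**What to change.** **Phase 3 (SAP 3.4.3.3).** Keep the two-visit rule as primary. Add to the by-LFU analysis a prespecified row, by arm, that also counts a single MAC-positive visit at LFU on any medium, labelled *unconfirmed, last visit*. Add one sentence stating that the two-visit by-LFU rate cannot include recurrences first detected at LFU. If Phase 3 has already been unblinded, SAP 1 requires the change to be identified as made after unblinding.

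**Phase 2 (SAP 3.4.2.1).** Present the same row as a supplementary analysis documented in the clinical study report, because SAP 1 limits changes after Version 2.0 to Phase 3.

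Replacing the primary rule at LFU is not advised. It would put two definitions along one cumulative series, and the EOT-to-LFU increase would then mix recurrence with a looser criterion.

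**Cost.** One sentence and one table row per phase, with no new data collection. Some single positives will be transient; the label and the two-visit figure alongside make that visible.
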